Certificate of Confidentiality

Participants are protected by a certificate of confidentiality, which ensures that we cannot turn over their personal medical information even if subpoenaed by a court order. An extension must be applied for whenever a certificate expires. Applications can be accessed here: https://public.era.nih.gov/commonsplus/public/coc/request/init.era.

Prior to submitting an application, the correct institutional official for the study must be identified.

Alternate Scenarios

1. Medical interruption: If a patient is medically unstable and unable to come in for study visits or taking study medication, the study physician may opt to place the patient on medical interruption rather than considering them a dropout from the study. A one-month medical interruption period is permitted in this study. If the patient is able to resume the study during this period of time, they should complete the next study visit that they would have completed on a normal schedule. If a patient cannot resume the study after one month, they should be brought in for an early termination visit if possible.

2. Early study medication termination: If a patient discontinues study medication prior to the week 12 visit, they should complete all week 12 measures and termination forms at their next visit.

3. When a patient is at risk of dropping out: When a patient is at risk of dropping out, study staff should assess the concern and take action accordingly. If a patient is at high risk for dropping out, all week 12 measures and procedures should be completed immediately to serve as an early termination visit in case the patient does not return for another visit. The duration of the study protocol can be accelerated by shortening visit intervals from 2 weeks to 1 week if the patient is past week 6. If the risk of dropout is due to a patient's increased agitation or difficulty sleeping, a study physician can prescribe lorazepam, up to 1 mg daily, as a rescue medication during the protocol.

4. Early study termination: Early study termination visits will include all measures and procedures that would be completed at a week 12 visit, including all biological samples. This visit will be entered in the database as a week 12/early termination, and for each form entered, the data enterer will be prompted to record which study interval they are closest to based on the number of weeks since randomization (e.g. weeks 2, 4, 6, 8, or 10).

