Outcome measures and covariates. Primary outcome: agitation/aggression score (domain score on the Neuropsychiatric Inventory (NPI), continuous measure from 0-12, longitudinal); Secondary outcome: response (dichotomous, based on 30% decrease in NPI core score (sum of domains for motor activity and agitation/aggression) plus a CGI-C score of much improved or very much improved, longitudinal); Exploratory outcome motor activity score on the NPI. Covariates/Predictor variables: 1) demographic characteristics (e.g., gender, race, age); 2) baseline measures of the corresponding outcomes. Other Measures:1) tolerability, as measured by emergent side effects (TESS scores and adverse events) over the course of the 12 week trial; 2) brain derived neurotrophic factor (BDNF) serum levels.

Sample size and randomization: The randomization will be carried out by the statistician and implemented by the pharmacist, who are both otherwise independent of the research team. The randomization sequences will be balanced in blocks of random size to prevent clinicians from guessing what the next patient's treatment might be.

Modeling longitudinal data and testing hypotheses. Modeling longitudinal data and testing hypotheses. All tests will be two-sided; α =0.05; intent-to-treat with data included for all patients with ≥1 post-baseline assessment. We will use generalized linear mixed models (GLMMs; SAS PROC GLIMMIX) for longitudinal data to evaluate study aims. Models will include fixed effects for treatment group, time, group x time interaction, and any baseline covariates found to be unbalanced despite randomization. Prior to analysis, we will examine all variables at all time points for outliers and inconsistencies and examine their distributions.⁴¹⁻⁴³

Primary hypothesis: *Lithium will significantly reduce agitation/aggression as compared to placebo.*

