The following linear mixed effects model will be used: $Y_{ij} = \beta 0 + \beta 1 I T R T + \beta 2t + \beta 3t^* I T R T + \beta 4X_i + \beta 4X_i$ bi + $\epsilon i j$ where Yij is the agitation/aggression score for the *i*th subject at *t*week, *t* =0, 2,...,12, *yi0* is agitation/aggression at baseline, *liTRT* is the indicator variable for randomized condition (placebo vs. lithium), an indicator of recruitment site (Columbia University Medical Center and Johns Hopkins School of Medicine), and any baseline covariates exhibiting imbalance after randomization, bi is a random intercept to account for repeated measures across time within the patient, and $\epsilon i j$ is a random error term. Significant interaction $t^* liTRT$ indicates that the changes in agitation/aggression in each treatment group is different over time (which corresponds to rejecting the null hypothesis that β 3= 0). The effect of time will be estimated for each group separately and the groups will be compared (using contrast) at the last time point t=12. Secondary hypothesis: Lithium will have greater proportion of responders compared to placebo. We will test whether the probability of response by end of active treatment differs significantly in the lithium and placebo groups by a chi-square test. In addition, we will test whether change in the probability of response differs across treatment groups by longitudinal analysis. We will use the generalized linear mixed effects model: logit(Yij) = $\beta 0 + \beta 1$ liTRT+ $\beta 2t$ + $\beta 3t^{*}$ /*iTRT*+ $\beta 4Xi$ + *bi* + ϵij where Yij is the a binary variable indicating response for the *i*th subject at t week, t = 2, 4, ..., 12. We will first test significance of the treatment effect by testing the group by time interaction.

Exploratory Hypothesis. Lithium will significantly reduce repetitive behaviors as compared to placebo. We will use the same model in the analyses for the primary hypothesis where Yij is the motor activity score for the *i*th subject at *t* week, *t* =0, 2,...,12.

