Tolerability: We will assess the tolerability of low dose lithium by assessing emergent side effects over the course of the 12-week trial on lithium compared to placebo. We will compute descriptive statistics of tolerability measures in each treatment group and provide both point estimates and their confidence intervals. We will test whether the change in TESS score from baseline to week 12 differs significantly in the lithium and placebo arms by a t-test.

Biomarker Hypothesis. Increases in BDNF serum levels will be associated with decreases in agitation/aggression and repetitive behaviors. The relationship between change in BDNF serum levels (defined as baseline minus endpoint of active treatment) and the changes in agitation/aggression score and motor activity score (defined as baseline minus treatment endpoint) will be tested using correlation analyses.

Power Analysis. Given the proof-of-concept nature of this study as a pilot, effect sizes with 95% confidence intervals rather than statistical significance testing will be the primary results of interest. The overarching aim is to demonstrate feasibility for conducting a larger trial which would then be used to adequately test efficacy.³³ Nevertheless, we provide some guidance regarding the statistical power available for testing differences between treatments. With n=60 patients randomized (30 to lithium, 30 to placebo) we conservatively examine power below assuming attrition will be 20% (i.e. 48 completers) though our past studies have all had attrition <20% and all available longitudinal data will be used for all individuals regardless of whether they complete the 12 weeks. For the primary outcome of agitation/aggression score measured by the NPI, we will have 80% power to detect a medium to large treatment effect size of 0.58-0.83 with the range depending on the within person correlation over time. Additionally, for responder status, we will have >80% power to detect a difference between, for example, a 15% response rate and a 50% response rate at 12 weeks. Differences among other exploratory outcomes and tolerability measures will be detectable with similar power.

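### The claimed power above 80% for 15% v 50% response is not reached with the plan's own 48 completers: the planned two-sided chi-square test has about 75-77%

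*Combined protocol and SAP*

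**What the plan says.** The Power Analysis section starts from 60 patients randomised equally to lithium and placebo. It sets the basis for what follows: "we conservatively examine power below assuming attrition will be 20% (i.e. 48 completers"). Two power statements come after that:

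- For the primary outcome, NPI agitation/aggression: "80% power to detect a medium to large treatment effect size of 0.58-0.83", the range depending on within-person correlation.
- For the secondary outcome, assessed at week 12: "for responder status, we will have >80% power to detect a difference between, for example, a 15% response rate and a 50% response rate".

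No separate sample size, test or formula is given for the responder statement.

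The test comes from the secondary hypothesis, which asks whether the probability of response by the end of active treatment "differs significantly in the lithium and placebo groups by a chi-square test". A longitudinal logistic mixed model is planned in addition. The level and the analysis set come from the section on modelling and hypothesis tests: "All tests will be two-sided; α =0.05; intent-to-treat with data included for all patients with ≥1 post-baseline assessment".

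**The concern.** The responder figure follows a sentence that fixes 48 completers as the basis, and the paragraph calls that basis conservative. A 35-point difference with about 24 patients per arm is near the edge of what a two-sided 5% chi-square test detects with 80% power, so the claim needed checking.

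If the true power on that basis is below 80%, the plan understates the risk of a false negative on response. The stated aim of the pilot is to show that a larger trial is feasible, and readers planning that trial may take the figure at face value. The same paragraph also claims similar power for the exploratory and tolerability outcomes.

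**Working it through.** **Inputs**

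- Patients: 48 completers of 60 randomised 1:1 (Power Analysis). I take 24 per arm; equal loss is my assumption and is varied below.
- Response rates: 15% and 50% (Power Analysis).
- Test: chi-square on two proportions (secondary hypothesis).
- Level: two-sided 0.05, so z = 1.96 (section on modelling and hypothesis tests).

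**Attempt to reproduce the stated figure at 24 per arm**

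*Pooled-variance formula, the usual approximation for the chi-square test.* The mean rate is (0.15 + 0.50)/2 = 0.325.

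- Standard error under the null: √(2 × 0.325 × 0.675 / 24) = 0.1352
- Standard error under the alternative: √((0.15 × 0.85 + 0.50 × 0.50) / 24) = √(0.3775 / 24) = 0.1254
- Power = Φ((0.35 − 1.96 × 0.1352) / 0.1254) = Φ(0.678) = **0.751**

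*Exact enumeration.* Summing Bin(24, 0.15) × Bin(24, 0.50) over all tables whose uncorrected Pearson statistic reaches 3.841 gives **0.767**.

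*Unpooled (Wald) formula.* Φ(0.35 / 0.1254 − 1.96) = Φ(0.831) = **0.797**.

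*Other two-sided methods.* Arcsine gives 0.766, Fisher's exact test 0.668, and exact enumeration with the Yates correction 0.640.

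No two-sided method tried at 24 per arm exceeds 0.80.

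**Unequal loss.** For splits of 48 from 20/28 to 28/20, power runs from 0.729 to 0.753 (pooled) and from 0.748 to 0.787 (exact Pearson). All are below 0.80.

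**Where 80% is passed (15% v 50%, two-sided 0.05)**

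| Per arm | Total | Attrition from 60 | Pooled | Exact Pearson |
|---|---|---|---|---|
| 24 | 48 | 20% | 0.751 | 0.767 |
| 25 | 50 | 17% | 0.769 | 0.790 |
| 26 | 52 | 13% | 0.786 | 0.809 |
| 27 | 54 | 10% | 0.802 | 0.820 |
| 30 | 60 | 0% | 0.843 | 0.847 |

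At 24 per arm, 80% power against 15% needs a lithium response rate of 52.3% (pooled) or 51.6% (exact).

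**Possible sources of the stated figure.** All 60 patients give 84.3% (pooled). A one-sided 0.05 test at 24 per arm gives 84.6%, but the plan says that all tests are two-sided. The documents do not show which calculation was used.

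**Basis of the neighbouring figure.** For a two-sample t-test, two-sided 0.05 and 80% power, the detectable standardised difference is 0.826 at 24 per arm and 0.736 at 30 per arm. The upper end of the plan's range, 0.83, agrees with the first. This suggests that the primary-outcome statement uses 48 completers.

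**The case against.** The strongest reply is that 48 is a deliberate floor and the responder test need not be confined to completers. The plan reports attrition below 20% in all its past studies and analyses everyone with at least one post-baseline assessment. Under Alternate Scenarios, "Early study termination visits will include all measures and procedures that would be completed at a week 12 visit". With 54 endpoints the test passes 80% by either method, and with 60 it has 84-85%. This stands as a statement about the power that the trial may achieve. It does not make the sentence right on the basis the paragraph sets. It also requires the 15% and 50% rates to hold in patients who leave early. If instead, as an illustration, 20% of each arm left and all were counted as non-responders, the rates at 30 per arm would be 0.8 × 15% = 12% and 0.8 × 50% = 40%, and pooled power would be 70.6%.

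A second reply is that response will also be analysed with a longitudinal model, which might have more power. The claim is worded as rates at 12 weeks, which is the chi-square comparison, and the plan gives no inputs from which the model's power could be worked out. The finding is accordingly limited to the chi-square test.

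A third is that the agreement at 0.83 is not unique. The range depends on unstated correlations, and a change-score calculation at 30 per arm could also give 0.58-0.83. This is fair: the match is supporting evidence only. The finding rests on the plan's own statement that power is examined on 48 completers.

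Finally, the gap is small and the rates are offered as an example. That bears on importance, not on whether the figure is correct.

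**Conclusion.** The concern holds. On the plan's stated basis of 48 completers, with its stated test and level, power for 15% v 50% is 75.1% (pooled) to 76.7% (exact), a shortfall of 3 to 5 percentage points. The figure stays below 80% for every split of 48 examined and under every two-sided method tried, although the unpooled formula comes within 0.3 points.

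The result assumes an uncorrected chi-square test and one endpoint per completer. Fisher's test or a continuity correction would lower the power further.

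The impact is modest. Response is secondary, the plan makes effect sizes with 95% confidence intervals its main results, and no sample size decision depends on this sentence. It is still a wrong figure that should be corrected.

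**What to change.** Replace the responder sentence with one that states its basis, for example: with 48 completers (24 per arm) and a two-sided 0.05 chi-square test, power is about 75-77% for 15% v 50% at 12 weeks, and 80% for 15% v about 52-53%.

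Alternatively, keep the claim of more than 80% and say that it needs at least 54 evaluable patients (27 per arm), the number that clears 80% by both the pooled and the exact calculation. If the figure was computed on all 60, say so, and state how patients who leave early are counted for response.

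In each case name the formula. The cost is one sentence and a slightly less favourable figure.
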